#### **Supplementary Analysis for both non-EMA and EMA registrations**

Subgroup (eg, region, age group, baseline AChEI status, baseline memantine status, and baseline MMSE subgroup) analyses will be performed for the subgroups defined in Section 5.3.4. The treatment effect within each subgroup and corresponding 95% CI for each co-primary endpoint will be summarized and also depicted using forest plot.

The treatment effect will be also examined using PP Analysis Set for each co-primary endpoint and analysis.

Descriptive statistics and graphical presentation for each co-primary endpoint will be provided.

Table 4 Primary Efficacy Analyses			
Score		Analysis for non-EMA Registration	Analysis for EMA Registration
MoCA	Primary	MMRM	Control based mean imputation with Mehrotra

	Sensitivity	As primary, but censor changes in AChEI medication	As primary, but censor changes in AChEI medication
	Supplementary	As primary, subgroups	As primary, subgroups
		As primary, Per Protocol Analysis Set	As primary, Per Protocol Analysis Set
CIBIC-Plus	Primary	GLMM	Proportional odds model with control-based pattern imputation
	Sensitivity	Censor changes in both AChEI and non-AChEI medications	Censor changes in both AChEI and non-AChEI medications
		Exclude subjects with changes/new AChEI and non-AChEI restricted medications	Exclude subjects with changes/new AChEI and non-AChEI restricted medications
	Supplementary	As primary, subgroups	As primary, subgroups
		As primary, Per Protocol Analysis Set	As primary, Per Protocol Analysis Set

#### 5.4.2 Secondary Efficacy Analyses

Table 5 Secondary Efficacy Analyses			
Score		Analysis for non-EMA Registration	Analysis for EMA Registration
CGIC-DLB	Secondary analysis	GLMM	Proportional odds model with control-based pattern imputation
	Additional secondary analysis	Proportional odds model with control-based pattern imputation	GLMM
CFI	Secondary analysis	MMRM	Control based mean imputation with Mehrotra
	Additional secondary analysis	Control based mean imputation with Mehrotra	MMRM

MMSE	Secondary analysis	ANCOVA and multiple imputation (MI) assuming MAR	ANCOVA and control-based pattern imputation
NPI	Secondary analysis	MMRM	Control based mean imputation with Mehrotra
	Additional secondary analysis	Control based mean imputation with Mehrotra	MMRM
MoCA	Additional secondary analysis	Control based mean imputation with Mehrotra	MMRM
CIBIC-Plus	Additional secondary analysis	Proportional odds model with control-based pattern imputation	GLMM

Table 5 details the analyses for the secondary endpoints. Further details are described below.

The CGIC-DLB scale will be analyzed as ordinal response data in a manner similar to the primary analysis of co-primary endpoint based on CIBIC-Plus, according to both methods for non-EMA and EMA registrations.

CFI is a continuous variable and will be analyzed in a manner similar to the primary analysis of co-primary endpoint based on MoCA, according to both methods for non-EMA and EMA registrations.

For the non-EMA registration, MMSE will be analyzed using ANCOVA with MI assuming MAR. For the EMA registration, MMSE will be analyzed using ANCOVA with control-based pattern imputation at subject level for missing data handling (Yang Yuan, Paper SAS270-2014, SAS Institute Inc.). The ANCOVA model will include corresponding baseline as a covariate, with treatment group and randomization stratification variables as factors.

NPI will be analyzed in a manner similar to the primary analysis of co-primary endpoint based on MoCA, according to both methods for EMA, and non-EMA registrations.

The details of calculating all efficacy endpoints are presented in Section 8.3 ALGORITHMS FOR EFFICACY PARAMETERS.

Additional secondary efficacy analyses will be performed with or without inclusion of efficacy data collected after treatment discontinuation:

- For the non-EMA registration, the change from baseline in the MoCA total score at 12 weeks will be analyzed using the control based mean imputation with Mehrotra as described above in Section 5.4.1 for the primary analysis for EMA registration. This analysis will be repeated for the CFI and NPI.
- For the EMA registration, the change from baseline in the MoCA total score at 12 weeks, change from baseline in the MoCA total score at Follow-up visit and other continuous variables will be analyzed using MMRM, as described above in Section 5.4.1 for the primary analysis for non-EMA registration. This analysis will be repeated for the CFI and NPI.
- For the non-EMA registration, the CIBIC-Plus scale at 12 weeks and other ordinal response variable (CGIC-DLB) will be analyzed using Proportional odds model with control-based pattern imputation, as described above in Section 5.4.1 for the primary analysis for EMA registration.
- For the EMA registration, the CIBIC-Plus scale at 12 weeks and other ordinal response variable (CGIC-DLB) will be analyzed using GLMM, as described above in Section 5.4.1 for the primary analysis for the non-EMA registration.

### 5.4.3 Exploratory Efficacy Analyses

The sleep endpoint (SCOPA-Sleep total score and subscores) will be analyzed in a manner similar to co-primary endpoint based on MoCA (according to both methods for non-EMA and EMA registration). Endpoints based on CIBIC-plus sub-items (Attention, Orientation, Memory, etc) rating will be analyzed in a manner similar to co-primary endpoint based on CIBIC-plus in the additional secondary analysis (GLMM,). The analyses of quality of life endpoints are described in Section 5.7 Other Analyses. MoCA subscores (Attention Vigilance, Abstraction Score, Orientation Score, Delayed Recall Uncued Score, Language Total, Naming Score and Visuospatial/Executive Score) will also be analyzed similarly to the total score in the primary analysis (according to both methods for non-EMA and EMA registration).

If data permit, the relationship between E2027 PD effects on CSF cGMP (and other biomarkers) and various efficacy endpoints will be explored using correlation analysis. The association between individual CSF cGMP concentration data and individual efficacy data within each treatment group will be examined through scatter plots. The scatter plots including the Pearson correlation coefficient and Spearman correlation coefficient will be produced for each treatment group for percentage change from baseline in CSF cGMP concentrations after 9 weeks of treatment and change from baseline at 12 weeks of treatment of the following efficacy endpoints:

MoCA total score and subscores

NPI total score, subscores and caregiver distress score

MMSE total score

CFI score

CIBIC-plus rating (1 – 7) as continuous variable.

Linear models within each treatment group may be fitted to further quantify the relationship between the changes in efficacy endpoints and the percent changes in CSF cGMP concentrations in case the above scatter plots suggested that the percent changes in CSF cGMP concentrations at 9 weeks of treatment may be predictive to later changes in efficacy endpoints.

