There are 2 coprimary endpoints which include a cognitive endpoint and a global clinical endpoint as recommended by regulatory guidelines for clinical trials on dementia. The primary endpoint on cognition is the MoCA, which is a composite cognitive endpoint evaluating various domains including attention, memory, executive function and visuospatial abilities. It has greater emphasis on executive functions, attention and visuospatial abilities known to be impaired in DLB and PDD (Biundo, et al., 2016) than MMSE. MoCA is less likely to show ceiling effect and is more sensitive in detecting early cognitive change in DLB than MMSE (Biundo et al., 2016). It showed similar rate of cognitive decline with MMSE in 1-year follow-up of DLB patients (Biundo et al., 2016). Moreover, it showed treatment benefit on cognition in a clinical trial of rivastigmine in PDD, indicating sensitivity to treatment effects of cognitive enhancing drugs (Li, et al., 2015). The coprimary endpoint on global clinical status is the CIBIC-Plus which evaluates global clinical impression of change from baseline by an independent rater who determines change in clinical status solely based on interview with the subject and caregiver or informant without reviewing efficacy and safety data obtained postrandomization. It showed overall clinical benefit in subjects treated with donepezil with PDD (Dubois, et al., 2012) and DLB (Mori, et al., 2012). The use of both coprimary endpoints (one on cognition and one on global clinical status) is consistent with regulatory guidelines for clinical trials in dementia such that if E2027 shows positive results on both coprimary endpoints, the study may be considered as a pivotal study in future regulatory submissions. Thus, in this study E2027 (50 mg QD) has to show statistically significant benefit on both the MoCA and the CIBIC-Plus for E2027 compared to placebo. If this is not achieved, but E2027 (50 mg QD) shows statistically significant benefit on at least the MoCA, then the result is considered positive for POC, but not a positive pivotal study, and additional pivotal studies will be conducted.

Other cognitive endpoints, including MMSE and CFI, are secondary endpoints. The MMSE is commonly used in clinical practice to document subjects' cognitive status and showed efficacy with donepezil in PDD (Dubois, et al., 2012) and DLB (Mori, et al., 2012; Ikeda, et

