### **Non-EMA Analyses**

#### **Co-primary Analysis of Change from Baseline in the MoCA Total Score at 12 Weeks for non-EMA registration**

Change from baseline in the MoCA total score at 12 weeks will be analyzed using MMRM. The MMRM model will include baseline variable (corresponding to the response variable in the model) as a covariate, treatment group, visit (Week 6 and Week 12), randomization stratification variables (receiving AChEI or not, geographical region [North America, Europe, Japan]), baseline variable-by-visit interaction, and treatment group-by-visit interaction as fixed effects. An unstructured covariance matrix will be used to model the covariance of within subject effect; if MMRM fails to converge then a covariance structure with fewer parameters from the following list will be employed according to the prespecified order in the list until the MMRM converges. The list of covariance structure will include Heterogeneous Toeplitz, Toeplitz, Heterogeneous Compound Symmetry, and Compound Symmetry. The Kenward-Roger approximation will be used to estimate the denominator degrees of freedom when unstructured covariance matrix is used. If MMRM fails to converge and a structured covariance matrix is used, the empirical method will be used to compute variance-covariance matrix of the fixed-effects parameters (sandwich estimator).

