### **Sensitivity Analysis of Change from Baseline in the MoCA Total Score at 12 Weeks for EMA registration**

A sensitivity analysis will be produced to repeat the primary analysis for MoCA but to censor data after changes in AChEI medications. For this the following missing mechanism will be added to the above reasons in the primary analysis

The effect had rescue medication not been made available to subjects prior to week 12 is not observable for subjects who initiated prohibited or restricted rescue medication. For these subjects, the data collected after initiation of prohibited rescue medication are assumed to contain no treatment effect in the E2027 treatment group. Technically, response data collected after initiation of new AChEIs or after any change in concomitant AChEIs stable dose will be treated as MNAR such that response data treated as MNAR in the E2027 treatment group would be imputed by the mean response in the placebo treatment group as described by the imputation method below.

In order to generate inputs for proposed primary and sensitivity analyses for the EMA registration, a MMRM will be used in separate MMRM analyses for each treatment group for all randomized subjects as well as completers assuming MAR for both treatment groups. The model will be adjusted for baseline MoCA, visit (Week 6 and Week 12), randomization stratification variables (receiving AChEI or not, geographical region [North America, Europe, Japan]), and baseline MoCA  $\times$  visit as fixed effects. An unstructured covariance matrix will be used to model the covariance of within subject effect; if MMRM fails to converge then a covariance structure with fewer parameters from the following list will be employed according to the prespecified order in the list until the MMRM converges. The list of covariance structure will include Heterogeneous Toeplitz, Toeplitz, Heterogeneous

Compound Symmetry, and Compound Symmetry. The Kenward-Roger approximation will be used to estimate the denominator degrees of freedom when unstructured covariance matrix is used. If MMRM fails to converge and a structured covariance matrix is used, the empirical method will be used to compute variance-covariance matrix of the fixed-effects parameters (sandwich estimator). The values of baseline MoCA will be adjusted using the overall baseline mean of all study subjects in computing least square (LS)-means.

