### Montreal Cognitive Assessment (MoCA)

This scale assesses different cognitive domains: attention and concentration, executive functions, memory, language, visuoconstructional skills, conceptual thinking, calculations, and orientation. It is reported to be useful to characterize global cognitive impairment in DLB. The MoCA scale is composed of 11 assessments. The following are the assessments and possible points earned for each assessment:

Visuoconstructional skills (0 – 5 points), Naming (0 – 3 points), Memory (No points), Attention: Forward/backward digit span (0 – 2 points), Attention: Vigilance (0 – 1 point), Attention: Serial 7s (0 - 3 points), Language: Sentence repetition (0 – 2 points), Language: Verbal fluency (0 – 1 points), Abstraction (0 – 2 points), Delayed recall (0 – 5 points), and Orientation (0 – 6 points).

The MoCA Total Score (range 0 to 30) = sum of all points earned. If any assessment is missing then the Total Score is missing. The lower the total score, the worse the cognitive impairment.

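### The exploratory MoCA subscores represent attention by one 0–1 vigilance item, leaving five of that domain's six points out of the subscore models and the CSF cGMP correlations

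*SAP*

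**What the plan says.** SAP 5.4.3 (Exploratory Efficacy Analyses) names seven subscores: "MoCA subscores (Attention Vigilance, Abstraction Score, Orientation Score, Delayed Recall Uncued Score, Language Total, Naming Score and Visuospatial/Executive Score". It adds that these "will also be analyzed similarly to the total score in the primary analysis (according to both methods for non-EMA and EMA registration". For the non-EMA registration the MoCA method in SAP 5.4.1 is: "Change from baseline in the MoCA total score at 12 weeks will be analyzed using MMRM". For the EMA registration it is control-based mean imputation, for which "a MMRM will be used in separate MMRM analyses for each treatment group for all randomized subjects as well as completers". SAP 5.4.3 also lists "MoCA total score and subscores" among the variables to be plotted against, and correlated with, the percentage change in CSF cGMP within each treatment group.

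SAP 8.3 sets out the points for each MoCA assessment. For attention it gives "Attention: Forward/backward digit span (0 – 2 points), Attention: Vigilance (0 – 1 point), Attention: Serial 7s (0 - 3 points". It defines the total: "The MoCA Total Score (range 0 to 30) = sum of all points earned". It gives no derivation for any MoCA subscore.

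Protocol 9.2 explains the preference for MoCA over MMSE: "It has greater emphasis on executive functions, attention and visuospatial abilities known to be impaired in DLB and PDD".

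**The concern.** Every other scored part of MoCA enters the subscore list whole: language as a total, visuospatial/executive as a block, and naming, abstraction, recall and orientation in full. Attention alone is cut to one of its three tasks, and the SAP gives no reason. That pattern looks like an oversight.

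Attention matters in this disease. Protocol 7.1 puts it first among the cognitive functions affected, and Appendix 1 describes attention deficits as possibly prominent and early. It is also one of the three domains cited in Protocol 9.2. If the MoCA total moves, or fails to move, the subscores are where a reader will look for the domain pattern. For attention that reader would find a pass/fail item. Its change from baseline can only be −1, 0 or +1, and a subject who passes at baseline cannot improve.

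**Working it through.** **Step 1: reproduce the plan's total.** Maximum points per assessment, from SAP 8.3: visuoconstructional 5, naming 3, memory 0, digit span 2, vigilance 1, serial 7s 3, sentence repetition 2, verbal fluency 1, abstraction 2, delayed recall 5, orientation 6.

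5 + 3 + 0 + 2 + 1 + 3 + 2 + 1 + 2 + 5 + 6 = 30, which matches the stated range of 0 to 30.

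**Step 2: sum the subscores listed in SAP 5.4.3.** Three labels differ from SAP 8.3 and are mapped by assumption: the language total is repetition plus fluency (2 + 1 = 3), visuospatial/executive is the 5-point visuoconstructional section, and uncued delayed recall is the 5-point recall section.

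| Subscore | Maximum |
|---|---|
| Attention vigilance | 1 |
| Abstraction | 2 |
| Orientation | 6 |
| Delayed recall, uncued | 5 |
| Language total | 3 |
| Naming | 3 |
| Visuospatial/executive | 5 |
| **Sum** | **25** |

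**Step 3: locate the gap.** 30 − 25 = 5 points. Digit span plus serial 7s is 2 + 3 = 5, so the gap is exactly those two tasks.

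**Step 4: size within the domain.** The attention maximum is 2 + 1 + 3 = 6. Kept: 1/6 = 16.7%. Left out: 5/6 = 83.3%.

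**Step 5: room to improve on vigilance.** If a proportion p pass at baseline, only 1 − p can gain a point, so the mean change cannot exceed 1 − p. The documents give no pass rate. As an assumption, for p from 0.5 to 0.9:

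| Assumed pass rate at baseline | Largest possible mean gain (points) |
|---|---|
| 0.5 | 0.5 |
| 0.7 | 0.3 |
| 0.8 | 0.2 |
| 0.9 | 0.1 |

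**Step 6: the cGMP correlations.** SAP section 4 expects about 48, 44 or 27 subjects with a final CSF sample, depending on dropout. Assuming an even split between arms, that is about 24, 22 or 14 per arm (48/2, 44/2, 27/2). A within-arm correlation of that size, with a variable that takes three values, says little about attention.

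**Step 7: effect of an attention total.** Replacing the 1-point item with a 0–6 score gives 25 − 1 + 6 = 30, so the seven subscores would account for the whole scale.

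**The case against.** The strongest reply concerns the reading. The list in SAP 5.4.3 consists of labels, not definitions, and several do not match SAP 8.3 word for word. SAP sections 9 and 11 place the derivation rules and table shells in separate documents, which may define an attention score. A comma may also have been dropped between attention and vigilance. With a full attention score, the list apart from vigilance would sum to 30. This is possible, and it is why the point is stated as a literal reading. But SAP 8.3 gives the single item the same name, so the literal reading is the more natural one, and specifications kept elsewhere do not change what the SAP lists. If a comma was intended, the text still needs correcting.

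The second reply is that little depends on these analyses. They are exploratory. MoCA subscores are not among the exploratory endpoints in Protocol 9.7.1.1.3 or SAP 5.1.3, no success rule uses them, and nothing requires subscores to sum to 30. Protocol 9.2 justifies MoCA as a composite and promises no domain analysis. SAP 5.8 would allow an attention score to be added later and labelled exploratory. All of this stands and keeps the priority low. A later addition, however, would be chosen after the results could be seen.

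Three stronger readings are tempting, and the documents support none of them:

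- A reader might infer that the trial cannot show an effect on attention. The CIBIC-Plus attention sub-item is a listed exploratory endpoint (SAP 5.1.3), and the CFI, a secondary endpoint, covers fluctuation in attention (SAP 8.3). These are interview- or caregiver-based and do not replace performance items, so the loss is confined to the MoCA attention domain.
- A reader might infer that digit span and serial 7s are discarded altogether. They count in full in the co-primary total.
- A reader might infer that the model is invalid. A change of −1, 0 or +1 has a mean, and the contrast estimates the difference in average net change. No bias or error inflation has been shown.

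**Conclusion.** The point holds in a limited form. Taken literally against SAP 8.3, the subscore list in SAP 5.4.3 covers 25 of 30 points, and all 5 missing points belong to attention, which is left with 1 of 6. This affects the exploratory subscore models under both registration methods and the correlations with CSF cGMP. It does not affect either co-primary analysis.

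The main defect is lost information in one domain; the awkward fit of a repeated-measures model of means to a pass/fail item is secondary. The 25-point sum rests on the label mapping stated in the working. The limit on the possible mean gain (0.5 down to 0.1 points) rests on an assumed baseline pass rate of 50% to 90%. This is a minor improvement, worth making because it costs almost nothing.

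**What to change.** Before unblinding:

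- In SAP 5.4.3, replace the vigilance entry with an attention total (0–6) = digit span (0–2) + vigilance (0–1) + serial 7s (0–3).
- Define it in SAP 8.3 as missing if any of the three components is missing, in line with the rule already given there for the MoCA total.
- Use it in the subscore models and in the CSF cGMP scatter plots and correlations.

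The cost is one derived variable from items already collected. No new data are needed, and the list stays at seven subscores, so no tests are added. If the team also wants vigilance on its own, a method for binary data would suit it better than a model of mean change.

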## 5.5 Pharmacokinetic, Pharmacodynamic, and Pharmacogenomic/Pharmacogenetic Analyses

The PK Analysis Set will be used for E2027 concentration listings and for summaries of E2027 concentrations in plasma and CSF by visit. A population PK approach will be used to characterize the plasma PK of E2027. For this approach, PK data from this study will be pooled with relevant data from Phase 1 studies. The PD Analysis Set will be used for the summaries and analyses of CSF PD biomarkers. The percentage change from baseline in CSF cGMP and any other PD biomarkers after at least 9 weeks of treatment with study drug post randomization will be analyzed and presented graphically. Summary statistics for CSF PD biomarkers will be summarized by visit. If data permit, a population PK/PD approach will be used to characterize the relationship between plasma and/or CSF exposures to E2027 and CSF PD biomarker levels. Further details on analyses of pharmacokinetic/pharmacodynamic data will be described in a separate PK/PD analysis plan.

Analyses of pharmacogenomic data will be described in a separate PGx analysis plan.

## 5.6 Safety Analyses

Evaluations of safety will be performed on the Safety Analysis Set. The incidence of AEs, out-of-normal-range laboratory safety test variables, abnormal ECG findings, and out-of-range vital signs, suicidality (C-SSRS), UPDRS-III, along with change from baseline in laboratory safety test variables, ECGs, and vital sign measurements (including orthostatic changes) will be summarized by treatment group.

Study Day 1 for all safety analyses is defined as the date of the first dose of study drug.

